5.1.3.2 Secondary Efficacy Analyses

Postoperative AT levels at the ICU admission will be summarized by treatment group. The analysis of covariance (ANCOVA) will be used to compare the treatment difference. ANCOVA model will include the AT level as dependent variable, treatment as fixed effect and baseline AT level as covariate. The similar approach will also be used to analyze the AT levels in other time points.

Postoperative chest-drain blood loss in the first 12 and 24 hours after surgery will be summarized by treatment group and will be analyzed using group t-test.

For transfusion requirements, Number of units of RBC, Number of units of FFP, and Number of units of platelets will be summarized by treatment group and analyzed using group t-test.

The number and percentage of subjects with each following procedure or morbidity will be separately summarized by treatment group and will be analyzed using Chi-square test (or Fisher Exact test as appropriate)

- Need for surgical reexploration
- Low cardiac output syndrome
- Myocardial infarction
- Stroke
- Acute kidney injury
- Arterial or venous thromboembolic events
- Infections
- Prolonged mechanical ventilation (>24 hours)

- All-cause postoperative mortality
- Prolonged ICU stay (>6 days)

Duration of ICU stay and the length of hospital stay will be summarized by treatment group. Non-parametric will be used to compare the treatment differences and Hodges-Lehmann estimation will be provided.

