3.1 Overall Study Design and Plan

[figure not shown]
This study will be a prospective, multicenter, randomized, double-blind, placebo-controlled study. Participating subjects will be 404 adult subjects undergoing cardiac surgery with CPB who will be randomized into two treatment groups preoperatively in a 1:1 ratio: AT-III (Human) treatment group and Placebo control group. All subjects will be stratified by their previous history of myocardial infarction (MI). Subjects undergoing complex/combined procedures will not be prescreened or screened for AT levels using local lab values to assess eligibility. Only subjects undergoing isolated coronary artery bypass graft (CABG) or single valve repair/replacements and not receiving preoperative heparin may be prescreened locally for AT levels (must be AT <80%).

Subjects randomized to AT-III (Human) treatment group will receive preoperative supplementation with AT-III (Human) designed to achieve an absolute increase (Δ) of 20% above pretreatment AT levels. Subjects randomized to Placebo control group will receive 0.9% Sodium Chloride (NaCl) for Injection, USP (United States Pharmacopeia).

The maximum study duration for a given subject will be approximately 7 weeks (48 days). There will be 2 weeks for prescreening screening, and randomization into one of the two study groups (AT-III [Human] treatment or Placebo control). After the 2-week prescreening and screening period, the cardiac surgery procedure will take place with the preoperative administration of AT-III (Human) or Placebo supplementation. After surgery, the subject will be admitted to the ICU and be followed for approximately 1 month (30 ± 4 days).

Both the primary efficacy endpoint (percentage of subjects with any component of the major morbidity composite) and the secondary endpoints will be evaluated for each subject after each cardiac surgery procedure, at the ICU admission, ICU discharge, and during a follow-up period of approximately 1 month (30 ± 4 days).

The overall study schema is shown in diagram below.

^a Randomization on Preoperative Visit (Day 0) may occur 24 hours before the day of surgery (Day 0).

^b If this visit coincides in time with the ICU discharge, the only assessments to be performed are those detailed in the ICU discharge visit. Regardless of when the ICU discharge takes place, AT activity levels should be measured on Postoperative days 1, 2, 3, and 5.

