4.2.2 Secondary Efficacy Variables

1. AT activity (levels) determinations:

To maintain the study blind, No unblinded AT concentration results will be provided to study sites or blinded Grifols personnel until after closure of the study database.

- a. AT activity levels will be measured for both AT-III (Human) treatment and Placebo control groups at the following time points:
 - Prescreening visit (local lab)*
 - Screening visit (local lab)*§
 - Screening visit
 - Preoperatively
 - Immediately before study drug administration
 - Immediately after study drug administration
 - Postoperatively at ICU admission
 - Postoperatively Day 1
 - Postoperatively Day 2
 - Postoperatively Day 3
 - Postoperatively Day 5
 - ICU discharge
 - 1-month follow-up visit

- * Only applicable for subjects undergoing isolated CABG or single valve repair/replacements (will be needed for eligibility only if subject not receiving preoperative heparin [see entry criteria]).
- § This AT (local lab) determination will not be required if the Prescreening visit is conducted.
- b. Percentage of subjects with AT levels of 58% or higher at the ICU admission will be calculated for both treatment groups and compared.

2. **Chest-drain blood loss** (mL) in the first 12 and 24 hours of chest closure is defined as the amount of blood collected in the cardiotomy reservoir from chest closure through the following 12 and 24 hours measured.
3. **Transfusion requirements** will be measured as the number of units of Fresh frozen plasma (FFP), red blood cells (RBCs), platelets (PLTs), cryoprecipitate, fibrinogen concentrate, prothrombin complex concentrates (PCCs), plasma, and whole blood from the day of ICU admission and throughout the follow-up period.

A specific perioperative transfusion algorithm will be applied:

Standardized Transfusion Algorithm

Red blood cells (RBC):

Administration of RBCs should be performed one unit at a time after which the hemoglobin (Hb) levels should be reanalyzed to check the suitability for the next unit.

- Hb <6.0 g/dL (≤ 3.72 mmol/L [millimoles/liter]): Transfusion is mandatory
- Hb = 6.0-8.0 g/dL (3.72-4.96 mmol/L): Transfusion is optional
- Hb = (8.0-10.0 g/dL). Transfusion is acceptable only if clinically justified*
- Hb >10.0 g/dL: Transfusion is not permitted.

* One or more of the following clinical justifications must be provided:

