- Central venous saturation (Swan Ganz / Central Venous Pressure (CVP) <60% with an arterial oxygen saturation of at least 90%.
- Cardiac Index <2.0 unresponsive to inotropic or mechanical support (catecholamine, intra-aortic balloon pump [IABP], etc.).
- Signs / symptoms of organ ischemia, such as: change in ST-segment or left ventricular wall motion abnormalities (LV).

Coagulation products:

Only if subject is bleeding 4 mL/kg/hour or more over at least 30 minutes or 1.5 mL/kg/hour or more over 2 consecutive hours.

- FFP (10-15 mL/kg) / PCC: If subject is actively bleeding and presents an international normalized ratio (INR) ≥ 1.5 .
- PLT: 1 apheresis unit or 4-6 pooled units if the PLT count is <100,000/ μ L.
- Cryoprecipitate / Fibrinogen concentrates: Administration of 8-10 units of cryoprecipitate or 2 grams of fibrinogen concentrate if the concentration of fibrinogen ≤ 1.5 g/L.

Shed blood collected during surgery can be retransfused according to institutional practice. Retransfusion of chest-drain collected blood is not permitted.

4. Percentage of subjects needing **surgical reexploration** defined as having to return to the operating room because of bleeding, tamponade, graft occlusion or any other cardiac reason will be considered from chest closure to the end of the follow-up period.
5. Percentage of subjects with **low cardiac syndrome** defined as the need for major inotropic support or intra-aortic balloon pump will be considered from the day of ICU admission and throughout the follow-up period.
6. Percentage of subjects with postoperative **MI** defined through enzymatic criteria plus new Q-waves at the electrocardiogram (ECG) will be considered from the day of ICU admission and throughout the follow-up period.

A perioperative MI is diagnosed by the following criteria:

- (0-24 hours postoperation):

The creatine phosphokinase-MB isoenzyme CK-MB (or creatine phosphokinase [CK] if MB not available) must be greater than or equal to 5 times the upper limit of normal, with or without new Q waves present in two or more contiguous ECG leads. No symptoms required.

- (>24 hours postoperation): Documented by at least one of the following criteria:

- a. Evolutionary ST-segment elevations
- b. Development of new Q-waves in two or more contiguous ECG leads
- c. New or presumably new left bundle branch block (LBBB) pattern on the ECG
- d. CK-MB (or CK if MB not available) ≥ 3 times the upper limit of normal

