10.2 Secondary Efficacy Analyses

All secondary efficacy analyses will be performed by treatment group based on the mITT population. No multiplicity adjustment will be performed.

All AT activity level data will be presented in listings. Postoperative AT levels at the ICU admission will be summarized. The analysis of covariance (ANCOVA) will be used to compare the treatment difference. ANCOVA model will include the AT level as the dependent variable, treatment as the fixed effect and baseline AT level (last available AT level from central laboratory before study drug administration) as the covariate. The same analyses will also be conducted for AT levels at other time points.

The number and percentage of subjects with AT levels of 58% or higher at the ICU admission will be summarized and compared with Chi-square test (or Fisher Exact test as appropriate).

Postoperative chest-drain blood loss in the first 12 and 24 hours after surgery will be listed, and will be summarized and analyzed using group t-test.

All data about transfusion requirements will be listed and summarized for the mITT population. Each blood product (e.g., RBCs, FFP, PLTs, cryoprecipitate, fibrinogen concentrate, PCCs, plasma, and whole blood) will be summarized separately and analyzed using group t-test. Cell saver blood use will also be analyzed. If the assumptions for parametric test are not met, the non-parametric test (Wilcoxon signed rank test) will be used. Shapiro-Wilk test will be used to test the normality.

Duration of ICU stay and the length of hospital stay will be listed and summarized. The non-parametric Wilcoxon rank sum test will be used to compare the treatment difference, and the Hodges-Lehmann estimate and 95% confidence interval (CI) will be provided.

Number and percentage of subjects with each following procedure or morbidity will be separately summarized and analyzed using Chi-square test (or Fisher Exact test as appropriate). Separate listings will be provided, except all-cause postoperative mortality which will be included in the listing of deaths. A separate eCRF page for Stroke was added while the study was underway, including questions of 'Had a stroke?', 'stroke number', 'stroke date/time', and 'stroke type'. For subjects without the Stroke page, all AEs will be evaluated for stroke events by the medical review.

- Need for surgical reexploration
- Low cardiac output syndrome
- Myocardial infarction (MI)
- Stroke
- Acute kidney injury (AKI)

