11.4 Physical Examinations

All physical examination data will be listed by subject.

Findings at the Screening Visit will be summarized with numbers and percentages by body system. Entries for 'Other' body systems will be grouped together; a subject with 2 or more 'Other' entries will be counted only once. Physical exam change findings after the Screening Visit will be summarized with numbers and percentages for each response category to the question 'Were there any new findings or existing findings that worsened?' ('No', 'Yes').

Abnormal findings judged by the investigators as clinically significant will be reported, analyzed, and discussed as AEs.

12 Interim Analysis

No interim analysis is planned.

13 Changes in Planned Analysis

Modified ITT (mITT) is added as a new analysis population and will be used for efficacy analyses that were planned to be conducted on ITT. The reason of this change is that the number of subjects who were randomized but not administered study drug is more than expected and the efficacy variables are complications and sequelae of complex cardiac surgery. Only subjects who are dosed and operated on should be evaluated.

Per protocol (PP) population will be based on mITT, not just ITT as originally planned.

Safety population will be used for demographic and baseline summary analyses which were planned to be conducted on ITT population. The reason of this change is that the number of subjects who were randomized but not administered study drug is more than expected.

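### SAP 10.2 names the Wilcoxon signed rank test, a paired or one-sample test, as the fallback for comparing transfusion units between two independent arms

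*SAP*

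**What the plan says.** SAP section 3.1 describes subjects "who will be randomized into two treatment groups preoperatively in a 1:1 ratio". Randomization is stratified by history of MI, and neither document describes matching, crossover or any other pairing. SAP section 3.2.2 lists transfusion requirements among the outcomes to be compared between the two groups. Section 4.2.2 measures them as units of each product, counted from the day of ICU admission to the end of follow-up.

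SAP section 10.2 analyses each blood product with a group t-test and then sets a switching rule: "If the assumptions for parametric test are not met, the non-parametric test (Wilcoxon signed rank test) will be used". The check that operates the switch follows at once: "Shapiro-Wilk test will be used to test the normality". The next paragraph deals with ICU and hospital stay and names a different test: "The non-parametric Wilcoxon rank sum test will be used to compare the treatment difference".

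Protocol section 5.1.3.2 has no non-parametric option for transfusion. It covers RBC, FFP and platelets, ending: "Number of units of platelets will be summarized by treatment group and analyzed using group t-test". SAP section 13, which lists changes to the planned analyses, does not mention the fallback.

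**The concern.** The signed rank test ranks within-pair differences, or the deviations of one sample from a fixed value. The rank sum test ranks two independent samples together. Only the second answers the question asked here, which is whether transfusion use differs between AT-III and placebo.

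This matters because the fallback may be the operative test for several products. The outcome is a count of units. Under the SAP's transfusion algorithm, coagulation products are allowed "Only if subject is bleeding 4 mL/kg/hour or more over at least 30 minutes" or at a lower rate sustained over two hours. Many subjects are therefore likely to have zero units of those products, and Shapiro-Wilk would then reject normality. The SAP's own rule would set the t-test aside and put an inapplicable test in its place. Whoever programs the analysis would have to depart from the written plan, possibly after unblinding, on outcomes related to bleeding, which the protocol's rationale names as a concern with AT supplementation.

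**Working it through.** The point is a mismatch between test and design and rests on no figure in the plan. The calculations below show how likely the fallback is to be triggered and what happens if the sentence is followed literally.

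**Size used.** The simulations use the SAP's 192 per arm (section 5.3). That figure reproduces. With 22.0% versus 14.3%, two-sided alpha 0.15 and 70% power, n = (1.4395 + 0.5244)² × (0.22 × 0.78 + 0.143 × 0.857) / 0.077² = 191.4, so 192. The SAP does not state sidedness; two-sided is what matches. The result does not depend on the transfusion test.

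**Is there anything to pair?**
- Between subjects: no. The arms are parallel, and an MI stratum is not a one-to-one match.
- Within subject: no. Units are counted only from ICU admission, so there is no baseline count.

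**How often would Shapiro-Wilk trigger the switch?** Assumptions: level 0.05 (the SAP gives none), 192 values, 2,000 data sets per scenario. Zero-inflated counts have a positive part of 1 + negative binomial (mean 2, dispersion 1).

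| Assumed distribution | Normality rejected |
|---|---|
| 50%, 70% or 88% zeros | 100% |
| Poisson mean 1, 2 or 5 | 100% |
| Poisson mean 8 | 99% |
| Poisson mean 10 | 89% |
| Poisson mean 12 | 77% |
| Poisson mean 15 | 60% |
| Poisson mean 30 | 27% |

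The switch is close to certain for low counts and not for high ones.

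**Literal reading 1: pair the arms.** This needs equal mITT arms. Starting from 202 per arm, with each subject retained independently with probability q, P(equal) = Σₖ [Bin(k; 202, q)]².
- q = 0.99: 0.207
- q = 0.95 (the SAP's 5% dropout): 0.092
- q = 0.90: 0.066

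Section 13 reports that "the number of subjects who were randomized but not administered study drug is more than expected", so equal arms cannot be counted on. With 190 versus 195 subjects the paired test would not run.

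If the arms did happen to be equal, the p-value would depend on the order of the rows. For 200 data sets with 50% versus 60% zeros and 500 random pairings each, the verdict at 0.05 differed between pairings in 75 of 200 (37.5%). In one such data set, over 1,000 pairings, p ran from 0.029 to 0.227; the rank sum test gives a single value, 0.029. In another data set, generated with no treatment effect, p ran from 0.45 to 0.99 against a rank sum p of 0.92.

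**Literal reading 2: one sample against zero.** Units cannot be negative, so with m transfused subjects all non-zero values are positive and the exact two-sided p is 2 × (1/2)^m. For m = 5 this is 0.0625; for m = 6 it is 0.031. Any arm with six transfused subjects is therefore significant at 0.05 whatever the treatment does.

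**The rank sum test.** With 192 per arm, 50% zeros and no effect, it rejected in 5.8% of 1,000 runs at a nominal 5%. The Monte Carlo standard error is √(0.05 × 0.95 / 1000) = 0.7 percentage points, so this is in line with its level.

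**The case against.** The strongest reply is that the intent is plain. The fallback stands in for a group t-test, section 10.2 says its analyses are by treatment group, and the rank sum test appears one paragraph later. A competent statistician would see the slip, and with unequal arms the paired test fails at programming instead of giving a wrong answer. This stands as an argument about severity. It does not make the sentence correct, and the section as written names two different Wilcoxon tests.

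Second, the t-test remains usable. Under zero fractions of 50%, 70% and 88%, 192 per arm and no effect, it rejected in 5.4%, 5.3% and 5.0% of 4,000 runs at a nominal 5%. That stands too and is a reason to leave the t-test as first line. But the SAP's rule discards the t-test when normality fails, so its robustness does not help once the switch is made.

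Third, the row-order and one-sample figures describe analyses nobody intends, and the distributions, the 0.05 levels and the way normality is checked are all assumed. The bleeding threshold governs coagulation products only; RBC transfusion follows hemoglobin bands, so the case for many zeros is weaker for RBC. These limits are accepted. The figures illustrate what literal compliance would mean and do not forecast an effect on the trial.

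**Conclusion.** The concern holds. The SAP's switching rule leads to a test that cannot compare two independent arms, and no other text in either document corrects it. It is most likely a slip of naming.

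The scope is the transfusion endpoints in section 10.2, which are secondary and carry no multiplicity adjustment. The primary CMH analysis and the sample size are untouched. That the rule would be triggered for most products is an inference from the type of endpoint, since the documents give no transfusion distribution; it is strong for low, zero-heavy counts and weak if mean use is high. That the named test is inapplicable rests on no such assumption. It should be fixed, though it does not threaten the trial's main conclusion.

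**What to change.** In SAP section 10.2, in the fallback sentence for transfusion requirements, replace *Wilcoxon signed rank test* with *Wilcoxon rank sum test*, the test the same section already uses for ICU and hospital stay. Make the change before unblinding so that it is documented as prespecified.

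Nothing else need change: the group t-test stays the first-line test for transfusion units and for chest-drain blood loss. The cost is a wording correction in one sentence, with no effect on data collection, patients or sample size.

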5.1 Data Handling

Unless otherwise noted, if an observation is missing at a specific scheduled visit/time point, the value at that visit/time point will not be imputed and will be set to missing.

Baseline in general will be defined as the last non-missing measurement taken prior to the start of the study treatment.

For ICU stay duration and length of hospital stay, if the discharge date is beyond the follow-up period and only ‘>1 month’ is recorded then it will be reported as is in data listings; and the date of last follow-up minus the ICU admission date or surgery date, respectively, plus 1 day or 34 days, whichever is longer, will be assigned for the statistical summary and analysis.

If a patient was mis-stratified with regards to myocardial infarction, the patient will be analyzed according to the correct stratum (accurate stratum).

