5.4 Randomization and Blinding

Subjects will be randomized into one of two treatment groups: AT-III (Human) treatment group and Placebo control group. Subjects will be stratified by their previous history of MI. Unblinded pharmacist or designee will obtain the treatment assignment based on a computer-generated randomization schedule.

To minimize the risk of unblinding, all subjects will receive the same total volume for all treatments with no visible differences in the external appearance of treatments, infusion bags will be covered with a non-transparent sleeve, and opaque intravenous (IV) tubing will be utilized. The unblinded study pharmacist, or designee, will prepare investigational product (i.e., AT-III [Human] and placebo) at each site. Monitoring of activated clotting time (ACT) for subject safety can potentially unblind an investigator if performed immediately before AND immediately after investigational product (IP) administration. Thus, to avoid potential unblinding, investigators should restrain from monitoring ACT values immediately before AND immediately after IP administration. Individual ACT determinations before OR after IP administration is not considered as potentially unblinding and is therefore permitted. However, if ACT monitoring is done prior to IP administration care must be taken to ensure blinded study personnel are not unblinded. Grifols Clinical Trial Materials personnel and Grifols Pharmacovigilance personnel will have access or be privy to treatment assignments.

Emergency unblinding instructions will be located in the Pharmacy Manual (to be used only if required).

Investigators must not draw any blood samples for AT levels outside the requirements of the protocol. Results from protocol-specified AT, thrombin-antithrombin complex (TAT), and prothrombin fragment 1+2 (F1+2) measurements will not be provided to the investigator or blinded sponsor personnel in order to ensure maintenance of the treatment blind.

6 Subject Disposition

Subject disposition will include the number and percentage of all subjects screened, in the populations of ITT (randomized), safety, mITT, and PP, and completing the study by treatment group and overall.

The number and percentage of subjects discontinuing from the study will be summarized by reason for discontinuation by treatment group and overall. The number and percentage of screening failures will be summarized for reasons of ineligibility.

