10.1 Primary Efficacy Analyses

Number and Percentage of subjects with any component of a major morbidity composite will be summarized by treatment and analyzed using Cochran Mantel Haenszel test adjusting for history of MI based on mITT population. Sensitivity analyses using PP population or mITT population minus subjects with postoperative AT administration per investigator's discretion will also be provided.

Subgroup analyses by age group, gender, and surgery type (isolated CABG vs. all other surgeries per medical review of all surgical procedures) will be performed for both mITT and PP populations, as well as mITT population minus subjects with postoperative AT administration.

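### None of the secondary tests adjusts for MI history, the randomisation stratum that the primary CMH test uses: a small, nearly free improvement, not an error

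*SAP*

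**What the plan says.** SAP 5.4 names one stratification factor: "Subjects will be stratified by their previous history of MI". SAP 10.1 carries it into the primary analysis, where the composite is "analyzed using Cochran Mantel Haenszel test adjusting for history of MI based on mITT population". SAP 5.1 settles what happens to a subject randomised in the wrong stratum: "the patient will be analyzed according to the correct stratum (accurate stratum").

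SAP 10.2 does not use the stratum again:

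- **Ten clinical outcomes:** each "will be separately summarized and analyzed using Chi-square test (or Fisher Exact test as appropriate"). AT of 58% or higher at ICU admission is compared in the same way.
- **AT levels:** "ANCOVA model will include the AT level as the dependent variable, treatment as the fixed effect and baseline AT level", with no MI term.
- **Chest-drain blood loss and transfusion units:** two-group t-test, with a rank-based fallback for transfusion.
- **ICU and hospital stay:** Wilcoxon rank sum without strata; "the Hodges-Lehmann estimate and 95% confidence interval (CI) will be provided".

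Protocol 5.1.3.2 is alike: the clinical outcomes "will be separately summarized by treatment group and will be analyzed using Chi-square test (or Fisher Exact test as appropriate"), and its other secondary tests have no MI term. SAP 13 adds no stratified secondary analysis. The secondary tests have no stated power, and "No multiplicity adjustment will be performed".

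**The concern.** A factor used to stratify randomisation is normally carried into the analysis. If it predicts the outcome and allocation is balanced within it, an analysis that ignores it overstates the variance of the treatment comparison. The test then becomes somewhat conservative and loses a little power. Here the composite would be tested with the stratum and its components without it, although MI history is already collected and a rule for the correct stratum already exists. What is at stake is some precision in the secondary results, and one analysis convention across the composite and its components. No secondary conclusion becomes invalid.

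**Working it through.** **1. The plan's own figure.** SAP 5.3 gives 22.0% versus 14.3%, alpha 0.15, 70% power and 192 per arm. Two-sided, with unpooled variance:

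n = (1.4395 + 0.5244)² × (0.22×0.78 + 0.143×0.857) / 0.077² = 3.857 × 0.29415 / 0.005929 ≈ 191.4, so 192 per arm.

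This reproduces. A one-sided calculation gives 122 and does not. Neither document states power for any secondary test, so everything below rests on assumed inputs.

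**2. Binary outcomes: set-up.** Assumed: relative risk 0.65, two-sided alpha 0.15 (the level in SAP 5.3), prior MI share f = 35%, control event rate r = 5, 10 or 15%, MI risk ratio k = 1, 1.8 or 3.4. Control risk is r/(1 - f + fk) without prior MI, and k times that with it. For r = 15% and k = 3.4 this is 0.15/1.84 = 8.2% and 27.7%. Treated risks are 0.65 times these. Pearson chi-square is compared with CMH, without continuity correction, over 400,000 simulated trials per scenario.

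**3. Power with 192 per arm, balanced within MI strata** (chi-square / CMH, %):

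| Control rate | k = 1 | k = 1.8 | k = 3.4 |
|---|---|---|---|
| 5% | 29.66 / 29.66 | 29.52 / 29.54 | 29.27 / 29.37 |
| 10% | 42.76 / 42.85 | 42.75 / 43.26 | 42.72 / 43.92 |
| 15% | 55.40 / 55.41 | 55.43 / 55.70 | 55.44 / 57.05 |

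The gain runs from 0.0 to 1.6 points. With prior MI at 20%, the 15% rate and k = 3.4, it is 57.03 - 55.32 = 1.7 points.

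**4. Power without exact balance.** Balance will not be exact: the mITT population drops undosed subjects, who SAP 13 says were more numerous than expected, and SAP 5.1 moves mis-stratified subjects. CMH minus chi-square, in points, for two illustrative splits:

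- Arms 188/193, k = 1: -0.20 at a 5% rate and -0.22 at 10%. With k = 1.8 at 10%: -0.04.
- Arms 195/184 with chance imbalance in the strata, 10% rate: -0.27 for k = 1 and -0.12 for k = 1.8.
- k = 3.4, both splits: about +0.5 at 10% and +1.2 to +1.5 at 15%.

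**5. True size at nominal 15%.** With balanced strata, 10-15% rates and k of 1.8-3.4, chi-square is at about 13.7-14.9% and CMH at about 15%. With chance imbalance (192/192, 15% rate, k = 3.4), chi-square is at 15.17%. At a 5% rate with equal balanced arms both tests are at 15.4-15.7%, which is discreteness; with 195/184 they are at 14.6% (chi-square) and 15.1% (CMH).

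**6. Linear models.** If MI strata differ by d standard deviations and a share p has prior MI, MI history explains R² = b/(1 + b), where b = p(1 - p)d².

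- p = 0.2, d = 0.2: 0.0064/1.0064 = 0.6%.
- p = 0.5, d = 0.5: 0.0625/1.0625 = 5.9%.

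At about 70% power and alpha 0.05, adjustment then adds 0.2 to 2.0 points. This applies to blood loss and transfusion units.

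The AT ANCOVA already holds baseline AT, so what matters is the partial R² given baseline AT. If MI history is unrelated to baseline AT, and baseline AT explains an assumed 40% or 60% of variance, 5.9% becomes 0.0588/0.6 = 9.8% or 0.0588/0.4 = 14.7%. If MI history acts through baseline AT, the figure is smaller. The documents do not say which.

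**7. Rank tests.** Van Elteren versus Wilcoxon, assuming log-normal data and a treatment shift of 0.2 SD: -0.2 to +0.2 points if the strata differ by 0-0.2 SD, and +0.8 to +1.6 at 0.5 SD (for example 67.0% to 68.2% with 35% prior MI).

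**The case against.** The strongest case against is that this is a preference. The planned tests are valid, the protocol and SAP agree, and the secondary analyses have neither stated power nor multiplicity control. A change between -0.3 and +1.7 points alters no decision, yet several methods must be rewritten. The top of the range also needs an MI risk ratio of 3.4, for which the documents give no basis, and neither Fisher's test nor an exact stratified test was simulated, nor any event rate below 5%.

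Most of this stands, and it is why the point is only one to consider. It does not remove the point, because the stratum is already collected, corrected and used for the composite, so the change costs almost nothing. For outcomes rarer than 5% no gain is claimed; there the reason to stratify is consistency with the primary analysis.

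Four stronger readings are tempting, and none is supported:

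- *The secondary tests are invalid or contradict the protocol.* They are valid, and protocol 5.1.3.2 omits MI history too.
- *Stratifying can never lose power.* It can lose up to about 0.3 points when MI history is not predictive and the arms are slightly unequal.
- *Chi-square is conservative here in general.* That holds at 10-15% event rates only with close balance within MI strata.
- *5.9% is a ceiling for what MI history adds to the AT ANCOVA.* It is a marginal R², and the partial R² can be larger.

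**Conclusion.** The point holds as a minor improvement. The omission is clear in both documents and covers every secondary test. For binary outcomes the effect of adjusting is about -0.3 to +1.7 points of power: roughly nil where MI history is weakly predictive, and up to about 1.7 where it is strongly predictive. Chi-square loses a little size (about 13.7-14.9% at nominal 15%) only under close stratum balance; with chance imbalance both tests are near 15%. For the AT ANCOVA no bound can be given.

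These figures depend on the assumed prior MI share, event rates, MI risk ratio, relative risk and alpha. The documents state none of these for the secondary outcomes.

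A reader might also infer that adjustment would make the component results line up with the composite. It would align only the stratification. Stroke counts as a thromboembolic event in SAP 4.2.2 but is a separate component in SAP 4.2.1, and the two mortality definitions use different windows.

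**What to change.** In SAP 10.2, before unblinding:

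- **Binary secondaries, including AT of 58% or higher at ICU admission:** CMH by the corrected MI stratum of SAP 5.1, with an exact stratified test when counts are sparse.
- **AT levels:** add MI history to the ANCOVA.
- **Blood loss and transfusion units:** a linear model with treatment and MI history.
- **ICU stay, hospital stay and any rank-test fallback:** van Elteren test. Either align the Hodges-Lehmann estimate and interval to the strata or label them as unstratified.
- **SAP 13:** record the change, and note that components and composite still differ in definition.

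The cost is SAP wording and minor programming, with no new data or patients. For binary outcomes that MI history does not predict, the power loss is at most about 0.3 points in the scenarios examined.
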